A crucial element of PROM development is the involvement of patients. This study will ground its development in existing qualitative research of rUTI patient experiences as well as conducting cognitive interviews with rUTI patients to obtain their perspective on whether the PROM questions are appropriate and valid for the population and their experiences of rUTI. Following this, pilot data collection of the PROMs alongside existing standardised measures of contextually relevant health aspects (e.g. pain) will be conducted to perform further statistical validity checks. The cognitive interviewing and piloting of the PROMs may include a mild risk of anxiety or discomfort due to the sensitive nature of some questions and need to reflect on potentially challenging experiences. Participants will maintain the right to withdraw at any point and will be encouraged to seek support from their GP/healthcare professional if needed.

Research Questions:

Primary aims:

1. To develop a patient-reported outcome measure of rUTI symptoms.
2. To develop a patient-reported outcome measure of rUTI impact.

Secondary aims:

1. To validate the rUTI symptom PROM by conducting statistical tests of its internal consistency, test-retest reliability, construct validity and criterion validity.

2. To validate the rUTI impact PROM by conducting statistical tests of its internal consistency, test-retest reliability, construct validity and criterion validity.

Design and Procedure:

An initial rUTI symptom scale and rUTI impact questionnaire have been developed based on existing qualitative research and literature review. The rUTI Symptom Scale includes a UTI-related symptom intensity subscale, and a UTI-pain intensity sub-scale. This PROM is designed to assess symptom intensity over the past 24 hours. The rUTI Impact Questionnaire includes a personal wellbeing subscale (covering psychological wellbeing and sleep/exercise disruption), a social subscale (covering social impact, isolation and anxiety), a work impact subscale, a sexual subscale (covering sexual impact and pain), and a patient satisfaction subscale. This PROM is designed to assess rUTI impact over the past two weeks.

A three-stage methodology will be employed:

(1) Expert screening for content validity

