score; and (5) homoscedasticity – (inspection of the standardised residuals plotted against standardised predicted values confirmed no violation).

Case-wise diagnostics of the subscale scores indicated five possible outliers outside 3SD; however, since these were not measurement errors and could feasibly reflect true variation within the population, they were not removed. Analyses conducted with and without these cases indicated that they had no statistically significant effect on the outcomes ($p > .05$).

Statistical analyses:

Exploratory factor analysis (EFA) was conducted for both the RUTISS and RUTIIQ data. Suitability for EFA was checked through bivariate correlation matrices with coefficients greater than .80 examined for potential multicollinearity (Field, 2013). Preliminary data analyses were undertaken to assess the factorability of the dataset using Bartlett's Test of Sphericity and the Kaiser-Meyer-Olkin Measure of Sampling Adequacy (Yong & Pearce, 2013). Principal Axis Factoring was selected for application above Principal Components Analysis and Maximum Likelihood Analysis to facilitate determination of a latent factor structure (Fabrigar et al., 1999; Yong & Pearce, 2013). Varimax rotation with Kaiser Normalisation was applied to minimise cross-loading of items on factors (Fabrigar et al., 1999). Visual inspection of scree plots determined the retained number of factors, combined with evaluation of eigenvalues exceeding Kaiser's criterion of 1 (Kaiser, 1960; Watkins, 2018). Items with extracted communalities less than .40 were removed, and a minimum factor loading of .40 was defined as acceptable a priori (Fabrigar et al., 1999; Watkins, 2018).

Internal consistency was measured for each finalised post-EFA RUTISS subscale and the RUTISS as a whole measure using Cronbach's alpha (Cronbach, 1951). To assess test-retest reliability, intraclass correlation coefficients (ICC) and their 95% confidence intervals were computed based on a single-rating, absolute-agreement, two-way mixed effects model, as recommended for test-retest reliability analysis of measures intended to demonstrate outcomes at an individual (single-rater) level (Koo & Li, 2016). Construct validity was assessed by computing the level of Spearman's correlation between each RUTISS subscale and the observed UTISA and NPRS scores (Schober et al., 2018).

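### Within each questionnaire's factor analysis, varimax works against its stated purpose if the factors correlate, and the .40 communality cut-off acts as a .63 loading cut-off for single-factor items

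*SAP*

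**What the plan says.** The SAP (Stage 3, Statistical analyses) states that "Exploratory factor analysis (EFA) was conducted for both the RUTISS and RUTIIQ data", which is best read as one analysis per questionnaire. On extraction: "Principal Axis Factoring was selected for application above Principal Components Analysis and Maximum Likelihood Analysis". On rotation: "Varimax rotation with Kaiser Normalisation was applied to minimise cross-loading of items on factors". That is the only reason given for the rotation. On item selection: "Items with extracted communalities less than .40 were removed, and a minimum factor loading of .40 was defined as acceptable a priori". The number of factors comes from scree plots, considered together with eigenvalues above 1.

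The Protocol (Design and Procedure) sets out the intended structure. The symptom scale has two subscales: "The rUTI Symptom Scale includes a UTI-related symptom intensity subscale, and a UTI-pain intensity sub-scale". The impact questionnaire has five: a "personal wellbeing subscale (covering psychological wellbeing and sleep/exercise disruption), a social subscale (covering social impact, isolation and anxiety), a work impact subscale", and then a sexual and a patient satisfaction subscale. Each instrument has a single recall period, 24 hours for symptoms and two weeks for impact.

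Neither document mentions an oblique rotation, an estimate of factor correlations, or a rule for items that load on more than one factor.

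**The concern.** There are two separate issues.

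The first is rotation. Symptom intensity and pain intensity over the same 24 hours, or wellbeing, social, work and sexual impact over the same two weeks, are facets of one condition and can be expected to move together. An orthogonal solution cannot represent that as a factor correlation, so it has to show it as cross-loadings, which is what the rotation was chosen to reduce.

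The second is item selection. One sentence of the SAP accepts a loading of .40 and removes items with communality below .40. For an item that loads on one factor these thresholds lie far apart, and the communality rule decides.

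The factor analysis settles which items form the final subscales, and later results build on them: "Internal consistency was measured for each finalised post-EFA RUTISS subscale and the RUTISS as a whole measure". The test-retest and construct validity analyses use subscale scores too. Items that came through the expert and patient stages could be lost to a cut-off stricter than the loading threshold a reader would take to be in force.

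**Working it through.** The two .40 cut-offs are rules, so there is no calculated figure in the plan to reproduce. Inputs from the documents are principal axis factoring, varimax, the two cut-offs, two planned symptom subscales and five planned impact subscales, and at least 132 recruited and 100 completing both parts (Protocol, stage 3). Factor correlations, loadings and item numbers are not given. They are assumed below.

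**Step 1: what varimax does to clean items.** Take two balanced factors with correlation φ and items with pattern loading λ on one factor and zero on the other. The orthogonal solution gives

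- primary loading = λ[√(1+φ) + √(1−φ)]/2
- cross-loading = λ[√(1+φ) − √(1−φ)]/2

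For example, with λ = .75 and φ = .5, the cross-loading is .75 × (1.225 − .707)/2 = .19.

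| Assumed φ | Primary | Cross-loading | Gap |
|---|---|---|---|
| .3 | .74 | .11 | .63 |
| .5 | .72 | .19 | .53 |
| .6 | .71 | .24 | .47 |
| .7 | .69 | .28 | .41 |

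An oblique solution would have zero in the third column. With five factors and λ = .70, the largest cross-loadings are smaller: .09, .14 and .20 at φ = .3, .5 and .7. Every cross-loading shown is below .40.

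**Step 2: the communality cut-off for single-factor items.** For such an item, communality = λ² under either kind of rotation.

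- λ = .40: .16, removed
- λ = .50: .25, removed
- λ = .60: .36, removed
- λ = .63: .397, removed
- λ = .64: .41, kept

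The break-even loading is √.40 = .632.

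**Step 3: sampling error.** Principal axis factoring was simulated with 12 clean items, two factors, φ = .5 and 300 runs. The share of items removed was:

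| True loading | n = 100 | n = 132 |
|---|---|---|
| .50 | 87% | 91% |
| .55 | 78% | 82% |
| .60 | 61% | 65% |
| .65 | 35% | 34% |
| .70 | 12% | 10% |

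Simulations with 18 items gave similar figures for a .60 loading at n = 132.

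**Step 4: when the .40 loading rule still operates.** In the orthogonal solution, communality is the sum of squared loadings. With k factors, an item at communality .40 has a largest loading of at least √(.40/k): .632 for k = 1, .447 for k = 2, .365 for k = 3, .316 for k = 4 and .283 for k = 5. With one or two factors, every item that passes the communality rule already exceeds .40, so the loading rule is redundant. With three or more it can act: .38/.38/.38 has communality 3 × .1444 = .433, passes the cut-off and fails the loading rule.

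**Step 5: cross-loaded items.** In the orthogonal solution, .46/.46 has communality .423 and is kept, .50/.40 has .41 and is kept, and .40/.40 has .32 and is removed. When a clean item and a cross-loader both have true communality .36 (n = 132, 18 items), removal rates are nearly equal: 66% to 70% for the clean item and 64% to 69% for the cross-loader. The cut-off does not see cross-loading at all.

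**The case against.** The strongest defence is that little is shown to go wrong in practice. No factor correlation is reported, so the correlated structure is an inference from content. The alpha for the whole symptom scale hints that its subscales are related, but the SAP also declines to compute a total across them. Even at φ = .7 the gap between primary and cross-loading is .41, so no illustrated item changes factor. Subscale scores are totals and remain free to correlate. Communality does not depend on rotation, so varimax cannot cause the deletions. A communality floor of .40 is a defensible conservative choice at 100 to 132 participants, and the two cut-offs are not contradictory: both must be met, and one is stricter for clean items. The SAP cites sources for its choices. All of this stands, and it limits the point. It does not supply the missing factor correlations, the missing cross-loading rule, or a reason for calling .40 acceptable when .63 is what counts.

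A reader might infer several stronger claims that the documents do not support:

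- **Orthogonality is imposed between symptoms and impact.** It applies only among the factors within each questionnaire.
- **The .40 loading rule never operates.** This holds for one or two factors. It fails for three or more, and five subscales are planned for the impact questionnaire.
- **The cut-off favours cross-loaders.** A .48/.48 item is removed far less often than a clean .60 item, but its true communality is .46 with uncorrelated factors, and .69 at φ = .5, against .36. At equal communality the difference disappears.
- **Too many factors were retained.** Eigenvalues above 1 used alone can over-extract, but the SAP has the scree plot determine the number, combined with eigenvalues.

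**Conclusion.** The point holds in two parts of different strength.

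On rotation, varimax works against its stated reason if the factors within a questionnaire correlate. The effect is modest, about .11 to .28 for two factors with a loading of .75 and assumed correlations of .3 to .7, and would seldom change item assignment alone.

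On item selection, the mismatch is arithmetic and needs no assumption about factor correlation: the working threshold for a single-factor item is about .63, not .40. How often a particular item is lost does depend on assumed loadings and item numbers; about two thirds for a true loading of .60 at n = 132 is an illustration, not an estimate for these questionnaires. Clean items well above .63 usually survive. The absence of a cross-loading rule is a plain gap.

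This is a cheap improvement to the analysis. It does not show that the final subscales are wrong.

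**What to change.** The two parts need separate changes, because changing the rotation leaves every communality as it was.

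1. Re-run both factor analyses with an oblique rotation (direct oblimin or promax). Report pattern loadings and factor correlations. If the correlations are near zero, the result should be close to the varimax solution and the existing choice is supported.
2. Retain items on a primary pattern loading of at least .40 plus a stated gap to the next loading, for example .20. The gap is a convention; what matters is that it is written down.
3. Treat communality below .40 as a flag for content review, not as automatic deletion.
4. List every item whose status or factor changes. For any change, repeat the alpha, intraclass correlation and Spearman analyses on the affected subscale.

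Parallel analysis may be added as a check on the scree plot, but it is not needed to correct this point.

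The cost is a re-run on existing data with different software options and a few sentences of SAP text. The downside is that the item list may change slightly.

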To obtain data to perform statistical validity checks of these two new PROMs among comparable other measures, a two-part online survey of adult rUTI patients will then be conducted. Parts 1 and 2, which will be separated by 24 hours which to allow for test-retest reliability assessment, will follow identical procedures (with the exception of Part 1 additionally including a demographics questionnaire). It is planned that a minimum of 132 participants will be recruited to take part in the online PROM data collection stage. A minimum of 100 participants will be

required to complete both parts, based on the COSMIN guidelines (Mokkink et al., 2018) and common practice for conducting exploratory factor analysis (Fabrigar et al., 1999). With an anticipated attrition rate of 25%, based on that found in a study examining retention rates in health outcome measure surveys (Hall et al., 2018), a minimum of 132 participants should be recruited to retain adequate statistical power.

The Part 1 online survey, built in REDCap, will start with a Participant Information Sheet and then Consent Form. Participants who wish to take part will be able to complete this survey virtually, e.g. from home. The Information Sheet is similar to the one used in the cognitive interviewing stage, except the procedure description is updated accordingly. In order to access the main study, the participant will be required to confirm their consent by ticking each item on the Consent Form page and providing an electronic signature. They will then access and complete a Demographics Questionnaire.

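### The eigenvalue-over-1 cut-off used to choose the number of factors ignores sampling error at n of 100 to 132; parallel analysis on both the reduced and unreduced matrices should replace it, with the scree plot kept as support.

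*SAP*

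**What the plan says.** The SAP, Stage 3, Statistical analyses, applies exploratory factor analysis (EFA) to both the symptom and the impact measure. On extraction: "Principal Axis Factoring was selected for application above Principal Components Analysis and Maximum Likelihood Analysis". On the number of factors: "Visual inspection of scree plots determined the retained number of factors, combined with evaluation of eigenvalues exceeding" a value of 1. Rotation is varimax. Two numeric item rules follow: "Items with extracted communalities less than .40 were removed", and "a minimum factor loading of .40 was defined as acceptable a priori".

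The SAP names no chance-based comparator, no second reader of the plot and no rule for when scree and eigenvalues disagree. It does not say whether the eigenvalues come from the unreduced correlation matrix or the reduced one (communality estimates on the diagonal). Nor does it say whether the number of factors was reconsidered after items were removed.

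The Protocol (Design and Procedure) plans 2 subscales for the symptom measure and 5 for the impact measure. Its stage (3) plans at least 132 recruited and at least 100 completing both parts.

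**The concern.** The communality and loading rules have stated cut-offs. The decision that precedes them, how many factors there are, rests on a visual judgement and a fixed threshold of 1. The eigenvalues of a p-item correlation matrix sum to p, so their mean is exactly 1. In any finite sample of unrelated items, some will exceed 1 by chance, and more so when n is small relative to p.

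Developing the two measures is the primary aim, and the number of factors fixes the subscales. Subscale totals, item removal, alpha, the test-retest intraclass correlation (ICC) and the validity correlations all follow from it. A spurious extra factor can split a real subscale; a missed one merges two.

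**Working it through.** **Sample size.** The Protocol's figure: 100 / (1 − 0.25) = 133.3, against 132 stated; 132 × 0.75 = 99. The gap of one or two participants does not matter here. The documents do not say which set of participants enters the EFA, so n=100 and n=132 are both used.

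**Rules compared.** Let λ₁ ≥ λ₂ ≥ … be the eigenvalues of the sample correlation matrix R.
- Eigenvalue over 1: count of λⱼ > 1, on unreduced R.
- Parallel analysis, unreduced: count the leading λⱼ that each exceed the 95th percentile of the j-th eigenvalue from random data with the same n and p.
- Parallel analysis, reduced: the same, after replacing the diagonal of R with squared multiple correlations, 1 − 1/rⁱⁱ, where rⁱⁱ is the i-th diagonal element of R⁻¹. This is the version matched to principal axis factoring.

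**Noise only.** No assumption about loadings is needed, only item counts.

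| Items | Mean largest eigenvalue, n=100 / 132 | Mean number over 1, n=100 / 132 |
|---|---|---|
| 12 | 1.61 / 1.53 | 5.6 / 5.7 |
| 20 | 1.89 / 1.77 | 9.1 / 9.2 |
| 30 | 2.20 / 2.02 | 13.4 / 13.6 |

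**With true factors.** The true numbers are the planned 2 and 5. The rest is assumed: 12, 20 or 30 items; loadings .4-.6, .5-.8 or .65-.85; factor correlation 0, .3 or .5; minor factors taking 0 or 20% of unique variance; five response categories. This gives 144 scenarios with 1,000 replicates each, so the simulation standard error of a single rate is at most √(0.25/1000) = 1.6 points.

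Averages over the 144 scenarios (equal weighting is arbitrary):

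| Rule | Correct | Too many | Too few |
|---|---|---|---|
| Eigenvalue over 1 | 29% | 71% | 0% |
| Parallel, reduced, 95th percentile | 68% | 23% | 9% |
| Parallel, unreduced, 95th percentile | 71% | 6% | 23% |

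The eigenvalue rule over-extracted in more than half of replicates in 104 of the 144 scenarios, and in 5% or fewer in 16. The reduced version beat it by more than 2 points in 122, tied in 17 and lost in 5.

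Selected scenarios at factor correlation .3, percent correct at n=100 / n=132:

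| Items / factors | Loadings | Minor factors | Eigenvalue over 1 | Reduced | Unreduced |
|---|---|---|---|---|---|
| 12 / 2 | .65-.85 | no | 99 / 100 | 100 / 100 | 100 / 100 |
| 12 / 2 | .5-.8 | no | 60 / 78 | 100 / 100 | 100 / 100 |
| 20 / 2 | .5-.8 | no | 2 / 9 | 100 / 100 | 100 / 100 |
| 20 / 5 | .65-.85 | no | 97 / 100 | 99 / 100 | 68 / 90 |
| 30 / 5 | .5-.8 | no | 0 / 0 | 96 / 99 | 77 / 93 |
| 30 / 5 | .5-.8 | yes | 0 / 0 | 34 / 15 | 71 / 75 |

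**Limits of the alternatives.** Over all scenarios with minor factors, the reduced version was correct in 57% (n=100) and 47% (n=132), against 66-68% for the unreduced. The unreduced version fails when five factors are strongly correlated: with 20 items, loadings .65-.85, correlation .5 and no minor factors, it was correct in 4% (n=100) and 9% (n=132), where eigenvalue over 1 was correct in 96% and 99%.

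**The case against.** The strongest reply is that none of these rates belongs to the SAP's rule. The SAP says the scree plot determined the number, with eigenvalues as a companion, and a careful reader of the plot may discard the small surplus factors that the cut-off admits. This stands. A mechanical largest-bend stand-in for the scree reading under-extracted in 56% of replicates. It is not a human reader, but it shows that the combined rule could err either way.

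Second, the loadings are assumed, and the SAP's own filter favours strong items. Under simple structure a communality of .40 is a loading of √.40 = .63, and (.632 − .5) / .3 = 44% of loadings spread evenly over .5-.8 fall below it. With loadings .64-.80 and no minor factors, the eigenvalue rule was right in roughly 50% to 100% of samples. This also stands, with a qualification: the SAP describes the filter as item removal, not as a step before the number of factors is chosen.

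Third, a reader might infer that the reduced version always wins, or that the cut-off is plainly mismatched to principal axis factoring. Neither is supported. The reduced version lost in 5 of 144 scenarios, and the SAP does not name the matrix. Had the cut-off been applied to reduced eigenvalues, the error would mostly be too few factors (26% under, 6% over).

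Fourth, the Protocol's minimum of 100 is for those "required to complete both parts, based on the COSMIN guidelines", and a reader might infer that the EFA was confined to them. The SAP nowhere says so.

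**Conclusion.** The point holds for the eigenvalue component. A threshold of 1 lies well below what chance alone produces at these sample sizes (mean largest noise eigenvalue 1.5 to 2.2). Used alone, it usually over-extracts with many items, moderate loadings or minor factors; with few, strongly loading items it does well. A chance-based cut-off is a better criterion on average, 68-71% correct against 29%.

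The size of the gain rests on assumed item counts, loadings, factor correlations and minor-factor variance. A reader might go further and conclude that the SAP's procedure over-extracted, or that the published subscales are wrong. The documents support neither: the error of the combined rule cannot be calculated, and no change in the actual number of factors has been shown. The change is worth making because every later psychometric result depends on the factor count and the remedy is cheap.

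**What to change.** Replace the eigenvalue-over-1 criterion with parallel analysis at the 95th percentile of at least 500 random data sets with the same n and number of items. Run it for each measure on both the reduced matrix (matched to principal axis factoring) and the unreduced matrix, with the scree plot as support.

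Name this as the primary rule before the re-analysis is run:
- If the two versions agree, use that number.
- If they differ, by one factor or more, treat them as the ends of a range. Choose within it by interpretability against the planned 2 and 5 subscales, and report the alternative solution with its subscale alpha and ICC.

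The cost is a few lines of code and a short SAP addendum. If the number changes, subscale totals, item removals, alpha, ICC and validity correlations must be recomputed. The rule for disagreement is needed because the two versions fail in opposite directions: too many factors when minor factors exist (reduced), too few when factors are strongly correlated (unreduced).

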Guidance by Willis on conducting and analysing cognitive interviews for questionnaire design and appraisal was followed (Willis, 2005; Willis, 2015). Anonymised verbatim transcripts of the interviews were created using speech-to-text software (Otter; <https://otter.ai>) with transcription errors manually corrected. The corresponding portions from every interview transcript for each PROM item were collated to create individual documents for each item containing all feedback pertaining to that question from across the entire sample. Top-down question feature coding was applied to these summaries using the Question Appraisal System (QAS-99) (Willis & Lessler, 1999). The systematic evaluation of every response to each PROM item for both the RUTISS and the RUTIIQ was conducted to identify potential problems, which were corrected based on verbatim quotes and interviewer field notes through collaborative analysis with the entire research team. If there were any uncertainties found in the first round of interviews about whether to include or exclude an item, the item was retained in the second round to gain further feedback. Further versions of the RUTISS and the RUTIIQ were created at this stage and used in the second interview round. The same process was undertaken after this, with an amended version created for pilot testing.

Stage 3: Online pilot testing

Data preparation and assumption testing:

Total scores were calculated for each of the Recurrent Urinary Tract Infection Symptom Score (RUTISS) subscales at Baseline and Test-Retest Assessments. Total scores for the RUTISS as a whole measure were not computed to avoid misrepresenting multidimensional constructs as a single score (Strauss & Smith, 2009). Data collected using the Urinary Tract Infection Symptom Assessment (UTISA) and Numerical Pain Rating Scale (NPRS) were scored according to their standard scoring systems.

The following assumptions were assessed: (1) normality – Shapiro-Wilk $p > .05$, so non-parametric analyses were conducted where applicable; (2) linearity – examination of scatter plots confirmed no violation; (3) multicollinearity – Variance Inflation Factor scores for the target label data as well as possible demographic characteristics were sufficiently close to 1; (4) independence of observations – Durbin-Watson statistic was approximately 2 for each subscale

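### The SAP declines a RUTISS total score as multidimensional but reports Cronbach's alpha for the whole measure, which can look acceptable even when the dimensions are unrelated

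*SAP*

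**What the plan says.** The SAP, Stage 3, under Data preparation and assumption testing, sets the scoring rule: "Total scores for the RUTISS as a whole measure were not computed to avoid misrepresenting multidimensional constructs as a single score". Scores are formed for each subscale only.

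Under Statistical analyses in the same stage, the reliability sentence covers both levels: "Internal consistency was measured for each finalised post-EFA RUTISS subscale and the RUTISS as a whole measure", with Cronbach's alpha as the coefficient. It gives no reason for the whole-measure coefficient and no threshold for judging any alpha.

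Three other statements bear on how that coefficient could be read:

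- **Rotation:** "Varimax rotation with Kaiser Normalisation was applied to minimise cross-loading of items on factors". Varimax is orthogonal, so no factor correlation is estimated.
- **Item retention:** "Items with extracted communalities less than .40 were removed, and a minimum factor loading of .40 was defined as acceptable a priori".
- **Number of factors:** "Visual inspection of scree plots determined the retained number of factors, combined with evaluation of eigenvalues exceeding Kaiser's criterion of 1". The resulting number is not stated. The protocol's Design and Procedure section describes two initial subscales: "The rUTI Symptom Scale includes a UTI-related symptom intensity subscale, and a UTI-pain intensity sub-scale".

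The listed analyses include no correlation between RUTISS subscale scores and no coefficient for a general factor. The correlation matrices that are mentioned serve to screen suitability for factor analysis.

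**The concern.** Cronbach's alpha is a function of the variance of an item sum. Computed over every RUTISS item, it describes the total that the scoring rule excludes. The two statements even name the same object, once to refuse it a score and once to report its internal consistency.

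The practical risk lies in interpretation. Alpha rises with the number of items, so several tight but unrelated subscales can together give a respectable value. Nothing else in the plan would tell a reader whether a high figure reflects a shared construct or only the strength of each subscale. Internal consistency is a named secondary aim in the protocol, and the measures are intended for assessing treatments. A later user who sees a good whole-measure alpha could take it as licence to sum the scale.

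**Working it through.** The documents state no alpha value, alpha threshold or RUTISS item count, so there is no figure of the plan's own to reproduce. The check asks what a whole-measure alpha would be if the dimensions had nothing in common.

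**Inputs**

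- Number of dimensions m: 2 in the protocol's initial scale. The post-EFA number is not given; assumed 2 to 4.
- Items per dimension p: not given; assumed 3 to 10, with equal-sized dimensions.
- Within-dimension item correlation r: assumed .4 to .7. The low end follows from the retention rule. If each item loads on one factor only, a communality of at least .40 means a squared loading of at least .40, and the product of two such loadings is at least .40.
- Between-dimension item correlation b: set to 0 as the limiting case.
- A value of .70 is used below as a mark for looking acceptable. This is an assumption; the SAP sets no mark.

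**Formula**

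Standardised alpha is k/(k−1) × [1 − trace(R)/sum(R)], with k = mp items. Here trace(R) = k and, with b = 0, sum(R) = k[1 + (p−1)r]. So

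alpha = k/(k−1) × (p−1)r / [1 + (p−1)r].

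**Worked cases**

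- 4 × 3 items, r = .4: 12/11 × 0.8/1.8 = .48
- 2 × 6 items, r = .5: 12/11 × 2.5/3.5 = .78
- 2 × 10 items, r = .7: 20/19 × 6.3/7.3 = .91

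**Whole-measure alpha with unrelated dimensions**

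| Dimensions × items | r = .4 | r = .5 | r = .7 |
|---|---|---|---|
| 2 × 3 | .53 | .60 | .70 |
| 2 × 4 | .62 | .69 | .77 |
| 2 × 6 | .73 | .78 | .85 |
| 2 × 8 | .79 | .83 | .89 |
| 2 × 10 | .82 | .86 | .91 |
| 3 × 3 | .50 | .56 | .66 |
| 3 × 5 | .66 | .71 | .79 |
| 4 × 3 | .48 | .55 | .64 |
| 4 × 5 | .65 | .70 | .78 |

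At r = .5, five items per dimension are enough to reach .70, whether there are two, three or four dimensions.

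**The figure can mislead in both directions.** The alpha of one subscale is pr/[1 + (p−1)r]. At r = .5 a three-item subscale has 1.5/2 = .75, yet four such unrelated subscales together give .55. A six-item subscale has 3/3.5 = .86, and two unrelated ones together give .78. Neither whole-measure value describes the subscale scores that are actually formed.

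**Sampling variation.** The protocol's minimum number completing both parts ("A minimum of 100 participants will be") was taken as the sample size. In 4,000 simulated samples of 100 with unrelated dimensions and r = .5, the observed alpha was at least .70 in about 97% for 2 × 6 items, 60% for 3 × 5 and 0.2% for 4 × 3.

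**A modest relation between dimensions.** With b = .2, sum(R) = k[1 + (p−1)r + (k−p)b]. At r = .5:

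- 4 × 3: 12/11 × (1 − 1/3.8) = .80
- 2 × 5: 10/9 × (1 − 1/4) = .83
- 3 × 5: 15/14 × (1 − 1/5) = .86

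A weak link between dimensions is thus enough to bring even the short scales above .70.

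**The case against.** The best defence is that the whole-measure alpha is a redundant descriptive figure. The appropriate analysis, alpha per final subscale, is already planned. Construct validity is assessed by subscale. No threshold, item-retention rule or conclusion depends on the whole-measure value, and the scoring rule already excludes a total. All of this stands, and it limits the severity.

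It is also fair that alpha is not an invalid statistic for multidimensional items. With uncorrelated errors it remains a lower bound to the reliability of their sum. The fault lies in reporting it for a sum that is not formed, and in the reading it invites. The SAP itself never claims that the RUTISS is one construct; it says the opposite.

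A reader might infer more than the documents support in three ways:

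- **That the whole-measure alpha is bound to look good.** The final item and factor counts are unknown, and short unrelated subscales give only about .55 to .69 at r = .5 (4 × 3 to 2 × 4).
- **That Varimax shows the RUTISS dimensions to be uncorrelated.** An orthogonal rotation constrains the factor solution. It does not show or assert that the subscale scores are unrelated, so zero correlation is a limiting case here and not the SAP's position.
- **That a favourable figure is already in hand.** The SAP is written in the past tense, but neither document reports an alpha value.

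**Conclusion.** The point holds. The scoring rule and the alpha sentence treat the whole RUTISS in incompatible ways, and the SAP offers no reason for the difference. That part rests on the text alone.

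The size rests on assumptions: 2 to 4 equal dimensions, 3 to 10 items each, r of .4 to .7 and no correlation between dimensions. Over that range the whole-measure alpha runs from about .48 to about .91, so it can look acceptable when the dimensions share nothing, but need not. It therefore cannot serve as evidence that the RUTISS measures a single construct consistently. Severity is minor to moderate.

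**What to change.** In the SAP, Stage 3, Statistical analyses, end the alpha sentence after the subscales and remove the reference to the whole measure. Report alpha for each final RUTISS subscale only, with the correlations between subscale scores alongside, so that readers can see directly how far the dimensions are related.

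The cost is one clause and one descriptive figure. The between-subscale correlations use scores the SAP already computes, so no new data are needed. If the whole-measure alpha has already been calculated, leaving it out of the report loses nothing about the scores in use.
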